3.3 Trial procedures

3.3.1 Schedule of Assessments

The schedule of assessments for the study is provided in Table 1, Table 2 and Table 3.

3.3.2 Study Procedure

For each visit, procedures and assessments are listed in the order in which they should be performed.

3.5 Discontinuation criteria

3.5.1 Discontinuation of donepezil dose escalation in individual subjects

For all patients, donepezil dose escalation will be discontinued if they manifest over a 24 hour period after study drug administration the following symptoms judged by the investigator as possibly or probably study-drug related:

- One (1) episode of vomiting, or
- Two (2) episodes of severe retching (separated by more than one hour on the same day), or
- One (1) episode of severe nausea (Grade 3; defined as nausea interfering with activities of daily living or inadequate oral caloric or fluid intake; tube feeding, total parenteral nutrition or hospitalization indicated) and/or severe abdominal discomfort (Grade 3; defined as severely interfering with activities of daily living), or
- Three (3) episodes of moderate nausea (Grade 2; defined as subjectively symptomatic, but not interfering with activities of daily living) and/or moderate abdominal discomfort (Grade 2; defined as interfering with function, but not interfering with activities of daily living) each on the same day, or
- One (1) episode of moderate diarrhea (Grade 2; defined as 4 to 6 stools more than at baseline).
- Any other circumstance that merits an adjustment in study drug dosage in the opinion of the investigator

3.5.2 Discontinuation of individual subjects from the entire study

During the study, the investigator or the sponsor may decide to discontinue a subject's participation in the study in the following cases:

- A protocol violation occurs;
- A serious or intolerable (other than those listed in the discontinuation of rivastigmine escalation criteria) AE occurs;
- The Sponsor or Investigator terminates the study.
- The subject requests to be discontinued from the study.
- The subject is non-compliant to any part of the study.
- The Investigator feels it is not in the best interest of the subject to continue in the study.

4 SELECTION OF SUBJECTS

4.1 Inclusion criteria

The criteria for inclusion that each subject must meet to be enrolled in the study are as follows:

- 1. Signed an Institutional Review Board (IRB) approved informed consent document indicating that they understand the purpose of and procedures required by the study and are willing to participate in the study and comply with all study procedures and restrictions. Informed consent must be obtained from the patient and/or a designated representative prior to initiating screening procedures to evaluate eligibility of the study.
- 2. Aged 50 89 years inclusive.
- 3. Meeting the diagnosis of probable AD consistent with:
 - Revised National Institute on Aging-Alzheimer's Association (NIA-ADA) criteria and
 - Diagnostic and Statistical Manual of Mental Disorders (DSM IV) criteria.
- 4. Of mild to severe severity (Mini-Mental Status Exam [MMSE] scores 7 24 inclusive).
- 5. Rosen-Modified Hachinski Ischemia Score of ≤ 4 .
- 6. Have a suitable caregiver to supervise the at-home administration of study drugs and observe for AEs.
- 7. Patients will be required to have been treated with donepezil 5 or 10 mg/day (given once daily) for at least 4 weeks just prior to Day1 for Population (group) 1 or;
- 8. Patients have never been treated with donepezil before (donepezil naïve) or who have not received any other AChEI for the past 6 months for Population (group) 2.
- 9. Patients must be in generally good health as indicated by their medical history and physical examination, vital signs, electrocardiogram (ECG), and standard laboratory tests.

4.2 Exclusion criteria

The criteria for exclusion of a subject from enrollment in the study are as follows:

- 1. Women of child bearing potential.
- 2. History or presence of a seizure disorder.
- 3. Current unstable peptic ulcer disease, urinary or gastric retention; asthma or obstructive pulmonary disease.
- 4. History or presence of bladder outflow obstruction, gastrointestinal obstructive disorder or reduced GI motility, or narrow-angle glaucoma.
- 5. History or presence of gastrointestinal, hepatic, or renal disease, or other condition known to interfere with the absorption, distribution, metabolism or excretion of drugs.
- 6. Renal and hepatic dysfunction with:
 - Total Bilirubin: >1.5 x UNL
 - AST: >2.5 x UNL

- ALT: >2.5 x UNL
- Serum Creatinine: >1.5 x UNL
- Creatinine Clearance: <30 mL/min
- 7. History or presence of myasthenia.
- 8. History or family history of Prolonged QT Syndrome.
- 9. History of unexplained syncope or family history of unexplained syncope or sudden death.
- 10. Myocardial infarction or hospitalization for congestive heart failure within 6 months.
- 11. ECG findings of:
 - Complete Left Bundle Branch Block;
 - Ventricular pacing;
 - 2nd degree or 3rd degree AV block;
 - Atrial fibrillation or atrial flutter;
 - HR <45 or >100;
 - PR >220 msec; or
 - QTcF >450 msec in male, >470 msec in female
- 12. Known hypersensitivity to donepezil, solifenacin or related drugs.
- 13. History of drug significant allergy.
- 14. History of substance abuse, known drug addiction, or positive test for drugs of abuse or alcohol.
- 15. Patients treated with the following medications within 8 weeks of screening
 - AChEIs (other than donepezil),
 - Peripherally acting anticholinergics (such as drugs for the treatment of overactive bladder disorder),
 - Psychoactive medications (including antipsychotics, antidepressants, anxiolytics or sedative hypnotics) having significant anticholinergic effects and/or believed to affect cognitive function.

Other medications are acceptable, at the investigators discretion, if dosage is held stable for at least 4 weeks prior to screening and throughout the study.

- 16. Patients considered unlikely to co-operate in the study, and/or poor compliance anticipated by the investigator.
- 17. Patients hospitalized within 4 weeks of screening.
- 18. Any other clinically relevant acute or chronic diseases which could interfere with patients' safety during the trial, or expose them to undue risk, or which could interfere with study objectives.
- 19. Patients who have participated in another clinical trial with an investigational drug within previous 30 days.
5 STUDY DRUG

5.1 Blinding

This is a single-blind study. The subject, caregiver, and site personnel who assess MMSE and ADAS-Cog are blinded.

5.3 Description of Study Drug

Version date: 07/22/2016

Placebo tablet

Placebo tablet is similar in size to donepezil 10 mg or solifenacin 5 mg/10 mg tablets.

5.3.2 Study drug manufacturing and labeling

Donepezil and solifenacin will be purchased by **a solution** from a licensed supplier of these pharmaceuticals.

The placebo tablet will be manufactured, packaged in bottle, labeled by Label will include the following information: protocol number, quantity of tablets, required storage conditions, lot number, name and address of the manufacturer and the following cautionary statement: New Drug – Limited by Federal law to investigational use.

5.3.3 Study drug storage, handling and disposal

At the site, all study drugs should be stored at room temperature **accessible** only to the designated qualified site personnel. All study drugs must be stored, inventoried and the inventories carefully and accurately documented according to applicable state, federal and local regulations, International Conference on Harmonisation (ICH) Guidelines, Good Clinical Practice (GCP) and study procedures.

The study drug is to be prescribed only by the Investigator or his/her named subinvestigator(s), and is to be used only in accordance with the protocol. The study drug must be distributed only to patients properly enrolled in the study.

The Investigator must keep an accurate accounting of the study drug received from the Sponsor, including the temperature of the storage area, the amount of study drug dispensed to patients, amount of study drug returned to the Investigator by the patients, and the amount returned to the Sponsor upon completion of the study. A detailed inventory must be completed for the study drug.

Unused study drug must be kept in a secure location for accountability and reconciliation by the study monitor. Investigator or designee must provide an explanation for any destroyed or missing study drug or study materials.

Unused study drug may be destroyed on site, per the site's standard operating procedures (SOPs), but only after the Sponsor has granted approval for drug destruction. The monitor must account for all study drugs in a formal reconciliation process prior to study drug destruction. All study drug destroyed on site must be documented. Documentation must be provided to the Sponsor and retained in the Investigator's study files. If a site is unable to destroy study drug appropriately, the site can return unused study drug to the Sponsor or designee upon request. The return of study drug or study drug materials must be documented.

5.4 Concomitant medication

5.4.1 Allowed Mediations

Dosage of allowed concomitant medication should be stabilized for at least 4 weeks prior to screening and should remain constant during the course of the study. Patients on concomitant memantine should be on a stable dose for at least 3 months. With the exception of medications listed in the exclusion criteria (Section 4.2) and in Section 5.4.2 below, concomitant medications will be allowed at the Investigator's discretion.

All concomitant medications and therapies (prescription and OTC) should be recorded in the CRF, with generic name (if known, otherwise brand name), indication, dose, route, frequency, and date(s) of administration. Any change in any of these parameters during the study should be documented.

5.4.2 Prohibited Mediations

Concomitant use of the following drugs is not allowed (such medications must have been discontinued at least 8 weeks prior to screening):

- peripherally acting anticholinergics (such as drugs for the treatment of overactive bladder disorder),
- psychoactive medications (including antipsychotics, antidepressants, anxiolytics or sedative hypnotics) having significant anticholinergic effects and/or believed to affect cognitive function

In addition, the following drugs are prohibited during the study:

- Strong CYP3A4 inhibitors
- Strong CYP3A4 inducers
- Strong CYP2D6 inhibitors

Patients who use prohibited medications during the study listed above may be discontinued from study drug. Medications prescribed after patients have discontinued the study drug will not be considered as prohibited medications.

Note: The discontinuation of a patient due to use of a prohibited medication is dependent upon the Sponsor's decision. The Investigator should contact the Sponsor prior to discontinuing a patient for disallowed medications.

6 ASSESSMENT OF PHARMACOKINETICS

6.1 PK Blood Sampling Schedule and Sample Analysis

The blood samplings will be performed at approximately 15 minutes before and 4 hours $(\pm 15 \text{ min})$ after study drug administration at each visits.

7 SAFETY ASSESSMENTS

7.1 Adverse Events

An AE is any untoward medical occurrence in a patient or clinical-investigation subject administered a pharmaceutical product that does not necessarily have a causal relationship with this treatment. A TEAE is defined as any AE that occurs after administration of the first dose of study drug. An AE can therefore be an unfavorable and unintended sign (including an abnormal laboratory finding), symptom, or disease temporally associated with the use of a medicinal (investigational) product, whether or not related to the medicinal (investigational) product. The failure of the anticipated pharmaceutical action of an investigational drug does not constitute a related AE.

AE rating

The condition of the subjects will be closely monitored throughout the study. The investigator will collect the AEs reported spontaneously, observed, or elicited in response to a non-leading question (for example, "How have you been feeling since we last asked you?"). The investigator will record all AEs in the source records and the CRF.

• The intensity/severity of an AE will be rated as follows:

Mild	: Awareness of signs or symptoms, but no disruption of usual activity.
Moderate	: Event sufficient to affect usual activity (disturbing).
Severe	: Inability to work or perform usual activities (unacceptable).

- The causal relationship of an AE to the study drugs will be rated as follows:
 - Not related : Temporal relationship of the onset of the event, relative to the administration of the product, is not reasonable or another cause can by itself explain the occurrence of the event
 - Unlikely : Is general, this category can be considered applicable to those AEs

related	which after careful medical consideration at the time they are
	evaluated, are judged to be unrelated to the study drug
Related	: AEs incontrovertibly related to the administration of the product.

Of the above definitions, AEs related to study drug are considered adverse reactions, while "unlikely" and "not related" do not represent a causal relationship.

- The action taken with the study drug for an AE will be rated as product withdrawn, not changed, not applicable. AEs requiring therapy will be treated with recognised standards of medical care to protect the health and the well-being of the subject.
- The outcome of an AE will be rated as recovered, recovering, not recovered, recovered with sequellae or fatal. The investigator will follow up any AE until it is resolved or until the medical condition of the subject is stable. All relevant follow-up information will be collected. For AEs that are ongoing at the last visit, the investigator will make thorough efforts to document the outcome.

7.2 Serious Adverse Events (SAE)

An SAE is any untoward medical occurrence that results in death, is life threatening, requires in-patient hospitalization or prolongation of existing hospitalization, results in persistent or significant disability/incapacity, or is a congenital anomaly/birth defect. In addition, important medical events that may not result in death, be life threatening, or require hospitalization may be considered a serious adverse drug experience when, based upon appropriate medical judgment, they may jeopardize the patient or subject and may require medical or surgical intervention to prevent one of the outcomes listed in this definition.

An AE is life-threatening if the subject is at immediate risk of death from the event as it occurs, i.e. it does not include a reaction that, if it had occurred in a more serious form, might have caused death. For example, drug-induced hepatitis that resolved without evidence of hepatic failure would not have been considered life-threatening, even though drug-induced hepatitis can be fatal.

An AE is incapacitating or disabling if the experience resulted in a substantial and/or permanent disruption of the subject's ability to carry out normal life functions.

7.3 Assessment of tolerability

The FID of each patient will be recorded.

7.4 Safety Laboratory Test

Blood samples will be collected as indicated in Table 1-4 for the following clinical laboratory tests:

Hematology: hemoglobin, hematocrit, red blood cell count, white blood cell count with differential (neutrophils, lymphocytes, monocytes, eosinophils, basophils) and platelet count.

Serum chemistry: calcium, sodium, chloride, potassium, blood urea nitrogen, glucose, total bilirubin, alkaline phosphatase, lactate dehydrogenase, aspartate aminotransferase, alanine aminotransferase, creatinine, calculated creatinine clearance, uric acid, phosphorous, total protein, albumin, and globulin.

7.5 Urinalysis

Urine samples will be collected as indicated in Table 1-4 for the following tests: glucose, bilirubin, ketones, specific gravity, blood, pH, protein, urobilinogen, nitrites, and leukocytes and, if necessary, microscopic examination.

7.6 Vital signs and body weight

Vital signs, including blood pressure, heart rate, respiratory rate, and temperature, will be measured after the patient rests in the supine position for at least 5 minutes.

Body weight will be measured as indicated in Table 1-4.

7.7 12-Lead ECGs

A standard 12-lead ECG will be recorded as indicated in Table 1-4. The Investigator will evaluate the ECG results as normal, abnormal, not clinically significant, or abnormal, clinically significant.

If QTcF on an on treatment ECG is \geq 500 msec then hold treatment and perform 3 repeat ECGs over 20-60 min; if the mean QTcF of the three ECGs is \geq 500 msec, withhold treatment and perform a repeat ECG the following day; if the QTcF has returned to baseline, dosing may resume.

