Cohort 2b	$1^{st} - 2^{nd}$ week: 10mg donepezil + 15mg solifenacin					
	3 rd week: 20mg donepezil + 15mg solifenacin					
	4 th week: 40mg donepezil + 15mg solifenacin					
	5th week: 60mg donepezil + 15mg (or 20mg) solifenacin					
Cohort 3b	$1^{st} - 2^{nd}$ week: 10mg donepezil + 15mg solifenacin					
	3 rd week: 20mg donepezil + 15mg solifenacin					
	4 th week: 60mg donepezil + 15mg (or 20mg) solifenacin					

*: The dose titration schedule of Cohorts 2 and 3 may be altered based on Cohort 1 result.

Per this amendment, all patients not treated with an AchEI for at least 6 months (Group 2) will receive 15mg solifenacin for 2 weeks before starting donepezil.

Each cohort will include approximately 6 patients donepezil-treated (Group 1) and approximately 6 patients not treated with an AchEI for at least 6 months (Group 2). Within each cohort, Group 2 patients will be enrolled only when at least 3 Group 1 patients have completed dose titration per protocol.

Patients will be enrolled in Cohort 2 only when patients enrolled in Cohort 1 have safely completed titration. Similary, patients will be enrolled in Cohort 3, only when patients enrolled in Cohort 2 have safely completed titration.

Cohorts 1 and 2 were completed prior to this amendment. This amendment is to change the dosing regimen of cohort 3. All subjects entering the study in cohort 3 will start with a dose regimen of 10mg donepezil + 15mg solifenacin and will continue to increase the donepezil dose by 5mg increments every 7 days (or up to 14 days per PI discretion) up to 40mg or the MTD.

Cohort 3c	1 st week: 10mg donepezil + 15mg solifenacin
	2 nd week: 15mg donepezil + 15mg solifenacin
	3 rd week: 20mg donepezil + 15mg solifenacin
	4 th week: 25mg donepezil + 15mg solifenacin
	5 th week: 30mg donepezil + 15mg solifenacin
	6 th week: 35mg donepezil + 15mg solifenacin
	7 th week: 40mg donepezil + 15mg solifenacin

Patients reaching their FID or having completed one week treatment with donepezil 60mg/day (40 mg/day for Cohort 3c), have two options.

- Option 1: Patient will be allowed to immediately enter a long term extension at their maximum tolerated dose (MTD) or MAD.

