3.2 Dose Escalation and Stopping rules

For all patients, donepezil dose escalation will be discontinued if they manifest over a 24 hour period after study drug administration the following symptoms judged by the investigator as possibly or probably study-drug related:

- One (1) episode of vomiting, or
- Two (2) episodes of severe retching (separated by more than one hour on the same day), or
- One (1) episode of severe nausea (Grade 3; defined as nausea interfering with activities of daily living or inadequate oral caloric or fluid intake; tube feeding, total parenteral nutrition or hospitalization indicated) and/or severe abdominal discomfort (Grade 3; defined as severely interfering with activities of daily living), or
- Three (3) episodes of moderate nausea (Grade 2; defined as subjectively symptomatic, but not interfering with activities of daily living) and/or moderate abdominal discomfort (Grade 2; defined as interfering with function, but not interfering with activities of daily living) each on the same day, or
- One (1) episode of moderate diarrhea (Grade 2; defined as 4 to 6 stools more than at baseline).
- Any other circumstance that merits an adjustment in study drug dosage in the opinion of the investigator

All those meeting one or more of the foregoing stopping rules will be withdrawn from dose titration and proceed in accordance with either of the two options given above.

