9.6 Compliance

Dosing information collected on the CRF will be listed for each subject. Compliance will be summarized by presenting the numbers and percentages of subjects receiving each dose of study drug.

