2. PROTOCOL DESIGN

2.1 Design Overview

This is a Phase II, ascending dose study of CPC-201 in patients with dementia of Alzheimer's type to determine the optimal dose titration schedule. The study involves a step wise cohort design in two different patient populations: Group 1 will consist of patients who have been treated with donepezil 5 or 10 mg/day (given once daily) for at least 4 weeks just prior to Day1. Group 2 will consist of patients who have never been treated with donepezil before (donepezil naïve) or who have not received any other

AChEI for the past 6 months.

Original Plan

Donepezil dose will be increased at weekly intervals, in accordance with the schedules given below, to its first intolerable dose (FID) or maximum allowed dose (MAD) 60 mg/day together with solifenacin 15 mg/day. If a patient does not tolerate a donepezil dose higher than 40mg/day with solifenacin 15 mg/day, the solifenacin dose can be increased to 20mg/day per the Investigator's decision.

Cohort 1	1 st week: 20mg donepezil + 15mg solifenacin 2 nd week: 30mg donepezil + 15mg solifenacin 3 rd week: 40mg donepezil + 15mg solifenacin 4 th week: 50mg donepezil + 15mg (or 20mg) solifenacin 5 th week: 60mg donepezil + 15mg (or 20mg) solifenacin
Cohort 2*	1 st week: 20mg donepezil + 15mg solifenacin 2 nd week: 40mg donepezil + 15mg solifenacin 3 rd week: 60mg donepezil + 15mg (or 20mg) solifenacin
Cohort 3*	1 st week: 20mg donepezil + 15mg solifenacin 2 nd week: 60mg donepezil + 15mg (or 20mg) solifenacin

*: The dose titration schedule of Cohort 2 and 3 may be altered based on Cohort 1 result.

Patients reaching their FID or having completed one week treatment with MAD, have two options.

Option 1: Patient will be allowed to immediately enter a long term extension at their maximum tolerated dose (MTD) or MAD.

Option 2: Patients may choose not to enter the long term extension, in which case the Investigator will decide whether the patient should discontinue high dose of donepezil without down-titration, or whether donepezil should be dwn-titrated to their own standard of donepezil dose. Whatever the decision, the patient will be treated at least an additional 7 days with solifenacin 15 mg/day.

First Amendment

After 8 subjects in Cohort 1 and 1 subject in Cohort 2 were enrolled, the protocol was amended to add Cohort 1b and to limit to enroll only Group 1.

Patients currently treated with donepezil (Group 1) will receive solifenacin 15 mg/day

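### After a confirmed mean QTcF of 500 msec or more, the visible protocol text lets dosing resume without limiting the dose, ending escalation or setting the FID

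*Protocol*

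**What the plan says.** Protocol 7.7 sets out a sequence for an on-treatment QTcF of 500 msec or more: hold drug and take three repeat ECGs; if their mean is also 500 msec or more, withhold drug and repeat the ECG the next day; and "if the QTcF has returned to baseline, dosing may resume". The wording is the same in all three protocol versions supplied, so it is not a leftover from an amendment.

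Escalation is governed by Protocol 3.2, repeated in 3.5.1. The list is introduced as "symptoms judged by the investigator as possibly or probably study-drug related". The named items are vomiting, retching, nausea or abdominal discomfort, and diarrhoea. One open item follows: "Any other circumstance that merits an adjustment in study drug dosage in the opinion of the investigator". Under 3.2, a patient who meets any item leaves titration. Protocol 3.5.2 separately permits, but does not require, withdrawal from the study, for example for a serious or intolerable adverse event or when "The Investigator feels it is not in the best interest of the subject to continue in the study".

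Protocol 7.3 says only that each patient's FID is recorded. SAP 2.4.1 makes each patient's FID and MTD the primary outcome. SAP 8.2 reports the proportions at each MTD level and tolerating 40 mg/day, and the mean highest dose reached. The MTD also has a clinical use, since under Protocol 3.1 (Option 1) "Patient will be allowed to immediately enter a long term extension at their maximum tolerated dose (MTD) or MAD".

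**The concern.** One drug-related vomiting episode ends titration and so marks the dose as not tolerated. A mean QTcF of 500 msec or more, confirmed on three ECGs and serious enough that the protocol itself orders drug withheld, is not on the same list. Its consequence for dose and for the FID is left open.

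Two things are at stake. The first is safety: the text does not prevent a return to the same dose, or a step up, after a confirmed event. The second is the primary outcome. Two patients with the same event and the same recovery can be recorded differently, one with that dose as the FID and the other as having tolerated it. The study is multicentre and has no data monitoring committee, and no visible rule brings these classifications into line.

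**Working it through.** The plan states no figure to reproduce: there is no formal sample size and no hypothesis test (SAP 3 and 5). The finding comes from reading the rules together; the arithmetic only shows scale.

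**Reading the rules together.** Suppose a Cohort 3c patient has a confirmed event at 40 mg and is back to baseline the next day.

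- If the investigator applies the open item in 3.2, titration stops. Taking the event dose as the FID and the MTD as the preceding dose (an assumption, since no definition is visible), the MTD is 35 mg.
- If the investigator does not apply it, 7.7 allows dosing to resume. The patient can complete the week at 40 mg, be counted as tolerating it, and enter the extension at that dose.
- If the event comes at a lower dose, the second route also leaves further escalation open.
- If the patient is withdrawn under 3.5.2, he or she may leave the MTD evaluable population, which SAP 6.2 limits to patients who completed titration.

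**Chance of at least one confirmed event.** The formula is 1 − (1 − p)^n. The per-patient risk p is assumed, because the documents give none. Entry QTcF is capped at 450 msec (men) and 470 msec (women), and the true risk may be zero.

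| p | n=4 | n=6 | n=12 |
|---|---|---|---|
| 0.5% | 2.0% | 3.0% | 5.8% |
| 1% | 3.9% | 5.9% | 11.4% |
| 2% | 7.8% | 11.4% | 21.5% |
| 5% | 18.5% | 26.5% | 46.0% |

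The chance that recording actually diverges is lower than these figures.

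**Choice of n.** The plan regards 4 to 6 evaluable patients per group per cohort as sufficient, with about 6 per group enrolled. SAP 2.1 says that at the first amendment "the protocol was amended to add Cohort 1b and to limit to enroll only Group 1", but it does not repeat this when it introduces Cohort 3c, and Protocol 3.1 still describes both groups. Using n=6 for Cohort 3c is therefore an inference, and n=12 is the alternative.

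**Effect of one event in Cohort 3c**, for a patient who would otherwise reach 40 mg (doses 10 to 40 mg in steps of 5):

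- Proportion tolerating 40 mg, with k of the others tolerating it: (k+1)/n − k/n = 1/n. This is 25 points at n=4, 16.7 at n=6 and 8.3 at n=12.
- If the patient leaves the denominator instead (n=6, k of the other five tolerating 40 mg): (k+1)/6 − k/5 = (5 − k)/30. This is 16.7, 13.3, 10.0, 6.7, 3.3 and 0 points for k = 0 to 5.
- That patient's MTD: 40 minus the preceding dose, from 5 mg (event at 40) to 30 mg (event at 15). The n=6 mean moves by 5/6 = 0.8 mg to 30/6 = 5.0 mg.
- That patient's highest dose reached: 40 minus the event dose, from 0 mg (event at 40) to 25 mg (event at 15). The n=6 mean moves by 0 to 25/6 = 4.2 mg.
- An event at 10 mg leaves no lower study dose to assign as the MTD.

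**The case against.** The best reply is that the open item already covers this. Withholding drug is naturally read as a dosage adjustment, so a confirmed event would end escalation under 3.2. Resumption in 7.7 is permissive and does not mention escalation. Many investigators would probably stop. That stands as a prediction of practice, but not as a requirement: 7.7 expressly provides for resumption after the hold, so an investigator who judges that no further adjustment is merited has followed the protocol.

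A second reply is that the event would be seen anyway. This largely stands. Under Protocol 9.6, "Dosing information collected on the CRF will be listed for each subject"; SAP 8.3.1.4.2 lists treatment-emergent clinically significant ECGs by subject; SAP 8.3.1 analyses safety by dose. A reader might infer that such events would be hidden, and the documents do not support that. What is missing is a link from a 7.7 hold to the FID/MTD tables. The dose-limiting listing in SAP 8.2 has no visible definition that would pull such holds in, and the action-taken categories in Protocol 7.1 include none for a temporary hold.

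Third, Protocol 3.4, the visit procedures, the assessment tables and SAP Appendix 1 are not visible, so a rule or an FID definition could sit there. This also stands and limits the point to the visible text. Sections 3.2, 3.5.1, 3.5.2, 7.3 and 7.7 contain no such rule and refer to none.

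A reader might also infer that a patient could enter the extension at whatever dose caused the event. That follows directly only at the 40 mg maximum. Below it, the extension opens only once an FID is reached, so entry at the event dose would need the next step up to be the FID.

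**Conclusion.** The point holds for the visible text. After a triplicate-confirmed mean QTcF of 500 msec or more, the plan neither limits the resumed dose, ends escalation nor sets the FID; those outcomes depend on investigator opinion or optional withdrawal. Followed as written, it permits the same or a higher dose, and it lets the dose that forced the hold be counted either way in the primary outcome.

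The size is conditional. No event rate is documented, and it may be zero. If one event occurs in Cohort 3c, the figure that matters is 1/n on the proportion tolerating 40 mg: 16.7 points at n=6, 25 at n=4, 8.3 at n=12. This assumes that the patient would otherwise reach 40 mg, stays in the denominator, and has the MTD taken as the preceding dose. The analysis is descriptive, so no formal test is affected. It would go too far to say that the protocol directs escalation after such an event, or that any patient was misclassified; the documents show only that the text allows either. The change is worth making but not critical, with medium confidence because of the unseen sections.

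**What to change.** (a) For any patient still to be titrated, add to Protocol 3.2 and 3.5.1: a confirmed mean QTcF of 500 msec or more under 7.7 ends dose escalation and sets that dose as the FID; once QTcF is back to baseline, dosing may resume only at a lower dose, and remains stopped if the event occurred at the first dose. The sentence should carry no separate relatedness judgement, because the qualifier used for the gastrointestinal items would bring back the discretion it is meant to remove.

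(b) In SAP 8.2, include withholdings under Protocol 7.7, with the donepezil dose at onset, in the dose-limiting side effect listing. If any occurred, show the MTD table both as recorded and with that dose counted as the FID.

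The cost is one protocol sentence, an addition to a listing already planned, and one further display only if there was an event, all from data already collected. The downside is slightly lower reported MTDs if an event occurs, including an occasional event not caused by drug. Part (a) cannot help patients already titrated and may be moot, since the SAP file is dated August 2017. Part (b) remains useful either way.
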